OFFICIAL TITLE OF STUDY: A Single-Session Intervention for Families on Waitlists for Child Anxiety Treatment

NCT NUMBER: NCT05841680

DATE: 10-15-2025

PROTOCOL

Youth with Anxiety Disorders on Waitlists for Treatment: A Critical Need

Anxiety disorders are among the most prevalent and impairing disorders in children and adolescents ("youth") (CDC, 2022). It is well documented that the mental health system is under-resourced and unable to meet the treatment needs of youth, including youth with anxiety disorders, creating a bottleneck problem for service providers (Kazdin, 2019). This bottleneck results in lengthy wait lists for services, spanning months and even years in some instances (Blech et al., 2017; Stallard et al., 2007; Steinert et al., 2017). These lengthy wait times prolong the distress and impairment experienced by youth with anxiety disorders and their families.

These data highlight the critical need to move beyond traditional services delivery approaches for youth with anxiety disorders. In making this move, there is urgency to develop and evaluate least restrictive interventions that are both accessible to families and do not place further burden on the already under-resourced mental health system. As a step towards addressing this need, we propose to develop and evaluate a least restrictive intervention for families on waitlists for treatment of youth anxiety.

Single-Session Interventions Delivered Remotely: A Promising Solution

Digital and telehealth methods offer promising approaches for developing least restrictive interventions because they reduce burden and increase accessibility (Comer & Myers, 2016). We build on our prior work and leverage both of these methods, digital and telehealth, in developing a remotely-delivered single session intervention (SSI) for families on waitlists for anxiety services. SSIs condense and deliver evidence-based interventions within a single session; their brevity opens new avenues to increase access to and efficiency of care, and decrease length and cost of care (Schleider & Weisz, 2017; Schleider, 2020). Emerging evidence supports the promise of SSIs as stand-alone treatments and adjunctive treatments (Hoyt et al., 2018), including for anxiety disorders in youth (Schleider & Weisz, 2017). Further, data support the acceptability of SSIs to clients on waitlists for psychological services (Schleider et al., 2020b). However, we are not aware of any SSIs that have been developed and evaluated for youth on waitlists for anxiety treatment.

Our own data also support the promise of digital and telehealth methods and SSIs as least restrictive approaches to treating youth anxiety. This includes randomized controlled trial data supporting the efficacy of digitally-delivered attention training (e.g., Pettit et al., 2020, 2022) and promising pilot data supporting the feasibility and acceptability of a telehealth-delivered single session psychoeducation intervention for youth who experienced a return of anxiety following positive response to cognitive-behavioral treatment (Cabrera et al., 2022). In this proposal, we build on these supportive data and extend our efforts to a novel impacted population, families on waitlists for treatment of youth anxiety.

Anxiety Management Support While Families Wait: A Novel SSI

Our primary goal in developing a SSI for families on waitlists for treatment of youth anxiety is to provide short-term reductions in anxiety symptom severity and impairment while families wait for more intensive treatment. A secondary goal is to explore whether a SSI could reduce families' need for more intensive treatment, meaning that families no longer feel the need to pursue more intensive treatment following completion of the SSI. We ground our proposed SSI in cognitive behavioral principles because cognitive behavioral treatments (CBTs) are the leading evidence-based approach for anxiety disorders in youth (Higa-McMillan et al., 2016).

Because it is not feasible to include all components of CBTs for youth anxiety in a SSI, we prioritize evidence-based components that are able to be understood and implemented by families following only a single session. This includes psychoeducation on the cognitive behavioral conceptualization of anxiety, introduction to self-regulation strategies to manage physiological manifestations of anxiety, and cognitive restructuring of anxiogenic thoughts. Given parents' important roles in facilitating implementation and practice of material presented in CBT approaches for youth anxiety (Silverman & Kurtines, 1996), we also will involve parents in the SSI and present strategies on how parents can support their children in managing anxious feelings and thoughts. In designing the module, we will leverage best practices for remotely delivered SSIs, including the use of engaging visual content with corresponding audio and interactive vignettes as well as comprehension checks (Schleider et al., 2020a). Details on the SSI components are provided in Methods.

Specific Aims

We will pursue the following aims in N = 60 families on waitlists for outpatient psychosocial treatment for youth anxiety.

Aim 1 Pilot Phase: Develop and pilot a SSI tailored for families on waitlists for outpatient psychosocial treatment for youth anxiety disorders. We will pilot the SSI with N=5 families and use cognitive response interviewing to obtain data from parents and children, ensuring the content is understandable and accessible. We will refine the SSI based on these data.

Following the Pilot Phase, we will enroll an additional N = 60 families and randomize them to either the SSI (n = 30) or waitlist control (n = 30)

Aim 2 Test Phase Acceptability, and Satisfaction: Examine acceptability of the refined SSI, as well as satisfaction with the SSI. We hypothesize that users will find the module to be acceptable and will report high satisfaction.

Aim 3 Test Phase Anxiety Outcomes: Demonstrate reductions in youth anxiety symptom severity. We hypothesize that anxiety symptom severity and impairment will be significantly lower among youth who receive the refined SSI relative to youth on waitlist control.

Approach

We will first pilot the SSI with five families and use cognitive response interviewing to obtain data from youth and parents, ensuring that the content is understandable and accessible. The SSI will be refined based on these data. Will then will evaluate the refined SSI in a sample of 60 youth participants and their parents. Participants recruited for this study will be youth 7-17 years old on waitlists at outpatient clinics to receive psychosocial treatment for anxiety disorders. Following an intake evaluation, eligible participants will be randomly assigned to one of two arms: the SSI (n=30) or the waitlist control (n=30).

Inclusion Criteria. (A) Be between ages 7 and 17 years; (B) endorse clinically elevated anxiety symptoms on either parent or youth report, as indicated by a score ≥ 25 on the Screen for Child Anxiety and Related Emotional Disorders-Child or Parent Versions (SCARED-C/P).

Exclusion Criteria. (A) parent report of past diagnosis of Autism Spectrum Disorder, Intellectual Disability, Bipolar Disorder, Tourette's Disorder, Psychotic Disorders, or Substance Use Disorders; (B) show high likelihood of hurting themselves or others; (C) not having access/connectivity needed for telehealth video conferencing to complete the module.

Procedures

Pilot Phase. Because our module integrates existing strategies and content found in evidence-based CBTs (see SSI Module below), our pilot phase prioritizes user experience (youths, parents) over expert content review. We will identify N = 5 families on our waitlist and administer the SSI module content to each youth-parent dyad. In cognitive response interviews, we will use verbal probing to ask youths and parents to provide feedback on module content (e.g., "what strategies do you find most helpful?, "which strategies were more difficult to understand?", "was there anything you disliked about the module?"), duration (e.g., "did you find the length of the module to be appropriate?"), and graphics (e.g., "was the module visually stimulating?", "what would help make module more interesting to view?"). We will use data obtained in these interviews to further refine the SSI module, ensuring clear and simple language that is accessible and engaging to youths and parents.

Test Phase. Upon contacting our outpatient clinic, parents will complete a screener to assess inclusion/exclusion criteria. Eligible youth and parents will then be presented with web-based assent/consent forms. Families who provide consent/assent will then complete the PRE evaluation consisting of demographics, SCARED-C/P and Child Anxiety Impact Scale – Child and Parent Versions (CAIS-C/P). Following completion of the PRE evaluation, families will be randomized immediately to either the SSI or waitlist control. Parents of the youth randomized to the SSI will receive a secure link via email containing the module and will be instructed to open it immediately. Both parent and youth will participate in the interactive module simultaneously. After completing the SSI, families will be granted access to view the module video an unlimited number of times and access to reference guides that summarize the module content.

Parents and youth will complete a POST evaluation one week after PRE and a Follow-Up evaluation four weeks after PRE. The POST and Follow-Up evaluations will consist of the same measures as the PRE evaluation, plus the Program Feedback Scale (PFS) and Client Satisfaction Questionnaire – 8 (CSQ-8) at POST and the Treatment Utilization Questionnaire at Follow-Up.

SSI Module

The module contains video segments presenting psychoeducation content and evidence-based practices for managing/reducing anxiety. Interactive exercises and comprehension questions are embedded throughout the module to

solidify understanding of concepts and correct misunderstandings. The module includes 4 main elements based on evidenced-based practices for managing/reducing anxiety (Higa-McMillan et al., 2016) and practices in single session intervention design (Schleider et al., 2020a).

- 1. Psychoeducation on the tripartite model of anxiety—how anxiety manifests itself through thoughts, feelings, and behaviors.
- 2. Psychoeducation and practice on self-regulation strategies to manage physiological manifestations of anxiety (i.e., feelings). Families will be introduced to "staying in the moment" and "relaxation strategies" and will have the opportunity to practice implementing the chosen strategy.
- 3. Explanation and practice of cognitive restructuring of anxious thoughts into neutral or realistic thoughts.
- 4. Evidence-based strategies on how parents can support their children in managing their anxious feelings and thoughts.

Measures

Primary Outcome.

Youth anxiety outcome measure completed by parents and youths. Screen for Child Anxiety Related Emotional Disorders—Child and Parent Versions (SCARED-C/P; Birmaher et al. 1997). The SCARED, child and parent versions, are 41-item rating scales that assess anxiety symptom severity. Items are rated on a 3-point Likert scale ranging from "Not true or hardly ever true" to "Very true or often true".

Primary Outcomes.

Youth anxiety impact measure completed by parents and youths. Child Anxiety Impact Scale – Child and Parent Versions (CAIS-C/P; Langley et al., 2004). The CAIS, child and parent versions, assess the impact of anxiety symptoms on the psychosocial functioning of youth. Items are rated on a 4-point Likert scale from "Not at all" to "Very much."

Intervention Acceptability measure completed by parents. The Program Feedback Scale (PFS; Schleider et al., 2020b). The PFS assess acceptability and user perceptions of web-based single session interventions. Seven items are rated on a 5-point Likert scale, ranging from "1" to "5" and participants are asked to share what the liked and what they would change about the intervention in an open-response format. A mean score of ≥3 indicates acceptability and positive program evaluation.

Treatment Satisfaction measure completed by parents and youths. The Client Satisfaction Questionnaire— 8-item version (CSQ-8; Larsen et al. 1979). The CSQ-8 is a widely used measure of satisfaction with mental health services (Sitzia, 1999).

Treatment Utilization measure completed by parents. Because families sometimes initiate alternative treatments during clinical trials, we will collect data on youths' usage of medication and/or psychosocial treatment at any point during their participation (Kolko, 2000). Additionally, we will collect data on whether or not families opted to remain on the treatment waitlist.

STATISTICAL ANALYSIS PLAN

Data management protocols will be used to ensure data integrity. Missing values will be estimated using full information maximum likelihood where applicable. A Holm modified Bonferroni correction will be used to control experiment wise error rate.

Aim 1: To examine the influence of the SSI on anxiety and anxiety impact (impairment), we will use two-way analyses of covariance in a structural equation modeling (SEM) framework (Rausch et al., 2003). We will use a maximum likelihood estimator with robust standard errors (MLR) as implemented in the MPlus 8.8 statistical software program. In each model, participant age, treatment condition, and the PRE-score on the outcome variable will be included as covariates. Robust likelihood ratio tests will be used to examine differences between PRE and POST mean scores and POST and FOLLOW-UP mean scores).

Aim 2: To examine acceptability, we will examine total mean scores of parents' responses on the PFS. A mean score \geq 3 indicates acceptability and positive program evaluation. To examine satisfaction, we will examine youth and parent total mean scores on the CSQ-8. Consistent with past studies (Larsen et al., 1979; Smith et al., 2014), we will categorize overall satisfaction ratings as "poor" (score = 8–13), "fair" (score = 14–19), "good" (score = 20–25) and "excellent" (score = 26–32).

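### Does Aim 2 need a confidence-limit rule before a mean Program Feedback Scale score of 3 or more is read as acceptable?

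*Combined protocol and SAP*

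**What the plan says.** In Specific Aims, Aim 2 is worded as a prediction: "We hypothesize that users will find the module to be acceptable and will report high satisfaction". The Measures section describes the Program Feedback Scale (PFS), which parents complete: "Seven items are rated on a 5-point Likert scale", followed by open-response questions. It then gives the benchmark: "A mean score of ≥3 indicates acceptability and positive program evaluation".

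The SAP paragraph for Aim 2 repeats that benchmark and sets out the analysis: "To examine acceptability, we will examine total mean scores of parents' responses on the PFS". Satisfaction on the CSQ-8 is handled in the same paragraph by sorting scores into four descriptive bands. Neither measure has a test, a confidence interval or a precision target.

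The Approach section assigns 30 families to each arm. The opening paragraph of the SAP states: "A Holm modified Bonferroni correction will be used to control experiment wise error rate". The Test Phase procedures place the PFS at the POST evaluation without naming an arm. Because the scale rates the module, SSI parents are the natural analysis set.

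**The concern.** A stated hypothesis appears to be settled by whether a point estimate reaches 3, the midpoint of a 1-to-5 scale, in a sample of about 30. With no allowance for sampling error, a true mean of exactly 3 would pass half the time, and a true mean slightly below 3 would pass fairly often. The SAP does control experiment-wise error elsewhere, so the absence of any error control here stands out.

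At stake is the wording of one conclusion. A mean of 3.05, say, could be reported as showing acceptability although the data are also compatible with a true mean below the plan's own benchmark.

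**Working it through.** The documents give no error rate, power or expected PFS mean for this benchmark, so there is no planned figure to reproduce.

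**Inputs**
- Benchmark: observed mean of at least 3 (Measures; SAP, Aim 2).
- n = 30 SSI parents (Approach), reading the benchmark as applying to the group mean.
- SD of a parent's mean score: not in the documents. Assumed 0.6 to 1.0.

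**1. How often the benchmark is met**

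P(observed mean ≥ 3) = 1 − Φ((3 − μ)/SE), with SE = SD/√30. This gives SE = 0.110 for SD 0.6 and 0.183 for SD 1.0. For μ = 2.9 the standardised distances are 0.1/0.110 = 0.91 and 0.1/0.183 = 0.55, giving 18.1% and 29.2%.

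| True mean | SD 0.6 | SD 1.0 |
|---|---|---|
| 2.7 | 0.3% | 5.0% |
| 2.8 | 3.4% | 13.7% |
| 2.9 | 18.1% | 29.2% |
| 3.0 | 50% | 50% |
| 3.25 | 98.9% | 91.5% |
| 3.5 | over 99% | over 99% |

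For the 3.25 row, 0.25/0.110 = 2.28 and 0.25/0.183 = 1.37.

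Sensitivity at a true mean of 2.9:
- SD 0.4 to 1.2: 8.6% to 32.4%.
- 24 completed forms (assumed), SD 0.6 to 1.0: 20.7% to 31.2%.
- Simulation of seven correlated items scored 1 to 5, with SDs of 0.62 to 0.96: 19.0% to 28.5%.

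**2. Width of the ambiguous zone**

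The 95% half-width is t(0.975, 29) × SE, with t = 2.045. It is 0.224, 0.299 and 0.373 for SD 0.6, 0.8 and 1.0. Only observed means between 3.0 and 3.22–3.37 both meet the benchmark and have an interval that reaches below 3.

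**3. Effect of requiring the lower 95% limit to exceed 3**

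Pass probabilities come from the noncentral t with 29 df and noncentrality (μ − 3)/SE.

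| True mean | SD 0.6 | SD 0.8 | SD 1.0 |
|---|---|---|---|
| 2.9 | 0.2% | 0.4% | 0.6% |
| 3.0 | 2.5% | 2.5% | 2.5% |
| 3.25 | 59.7% | 38.0% | 26.3% |
| 3.5 | 99.3% | 91.1% | 75.4% |
| 4.0 | over 99.9% | over 99.9% | over 99.9% |

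The rule nearly removes false passes just below 3. In exchange, a module whose true mean is 3.25, above the plan's own benchmark, would fail to earn the label 40% to 74% of the time (100 − 59.7 and 100 − 26.3). Near 4 the two rules agree.

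**4. Interaction with the Holm correction**

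The lower-limit rule is a test. The PFS is listed under primary outcomes, so it would have to be decided whether this test joins the Holm family. If it joined four anxiety tests (parent and child versions of two scales; an assumption), the strictest step would be 0.05/5 = 0.01. The observed mean would then have to reach 3.30–3.50, and a true mean of 3.5 would pass between 96% (SD 0.6) and 50% (SD 1.0) of the time.

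**The case for a change.** The strongest reply is that the plan pairs the benchmark with an explicit hypothesis, so it works as a decision rule whatever it is called. Even a purely descriptive mean from 30 people deserves an interval. The remedy needs only SAP wording, would label the middle zone inconclusive and not unacceptable, and costs almost nothing if scores are near 4. No expected PFS mean is stated, so the plan cannot simply count on a comfortable result.

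Part of this stands. The benchmark does carry no measure of precision, and a mean barely above 3 should be described with caution.

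It does not establish a defect that needs amending, for four reasons:
- The SAP says the means will be examined. It places the benchmark beside the CSQ-8 bands, which are also descriptive. No progression step, sample size or treatment decision depends on the result.
- The Holm commitment is not breached. It governs tests, and Aim 2 plans none.
- The 18–29% figure depends on an SD from outside the documents and on a true mean only 0.1 point below the cut-off. At 2.8 the pass rate is already down to 3–14%.
- The benchmark could also be read as applying to each parent's seven-item mean. On that reading the figure does not describe the plan at all.

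**Conclusion.** No change to the plan follows. With n = 30, an assumed SD of 0.6 to 1.0 and the group-mean reading, the observation is numerically correct: a true mean of 2.9 meets the benchmark in 18–29% of trials. Its reach is limited to observed means between 3.0 and about 3.22–3.37, and to the wording of one descriptive statement.

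The lower-limit rule exchanges one error for another. It cuts passes at a true mean of 2.9 to 0.2–0.6%, but lowers them at 3.25 from 91–99% to 26–60%. The documents give no ground for weighting false acceptance that heavily, and the rule's place in the Holm family would be left open.

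The milder options are to print a confidence interval beside the mean or to name the SSI arm as the analysis set. Both are details a competent analyst supplies when reporting: waitlist parents have not been given the module to rate, and the interval follows from the mean, SD and n. Neither would change a conclusion drawn under the plan's benchmark.

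### With 30 families per arm, uncorrected MLR tests of condition reject somewhat more than 5% under the null, so the p-values entering Holm are slightly too small

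*Combined protocol and SAP*

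**What the plan says.** The Approach section randomises 60 families, 30 to each arm. Outcomes are measured again at one and four weeks: "Parents and youth will complete a POST evaluation one week after PRE and a Follow-Up evaluation four weeks after PRE" (Procedures, Test Phase).

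The SAP, under Aim 1, plans two-way ANCOVA in a structural equation model. On estimation it says "We will use a maximum likelihood estimator with robust standard errors (MLR) as implemented in the MPlus 8.8 statistical software program", and on the regressors "In each model, participant age, treatment condition, and the PRE-score on the outcome variable will be included as covariates". The only test it names is for change over time: "Robust likelihood ratio tests will be used to examine differences between PRE and POST mean scores and POST and FOLLOW-UP mean scores". The opening paragraph of the SAP adds "Missing values will be estimated using full information maximum likelihood where applicable" and "A Holm modified Bonferroni correction will be used to control experiment wise error rate".

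The SAP does not state the test statistic for condition, its reference distribution, alpha, sidedness, or which tests form the Holm family.

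**The concern.** MLR standard errors and robust likelihood ratio tests are justified in large samples. With 60 families two approximations work in the same direction. The sandwich variance is not corrected for the mean parameters already estimated, and a normal reference ignores that the variance itself is an estimate. Both make p-values too small and intervals too narrow.

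Holm is the plan's only stated error control, and its guarantee requires each p-value that enters it to hold its level. The relative excess also grows at the stricter thresholds that Holm applies first. The hypothesis under Aim 3 of the protocol is worded as a significant difference between arms, so a result near the threshold could be read the wrong way.

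**Working it through.** The plan gives no error rate, power or effect size, so it has no figure of its own to reproduce.

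**Inputs from the documents.** n = 60, 30 per arm (Approach). Intercept, age, condition and PRE score give k = 4 mean parameters (SAP, Aim 1).

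**Assumed, because not stated.** Two-sided alpha 0.05; normal or chi-square reference; n = 48 to represent 20% loss; Holm thresholds of 0.0125 and 0.00625 for families of four or eight tests.

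**Step 1: Wald z, closed form.** With normal errors the maximum likelihood variance divides by n rather than n-k, so z = t × sqrt(n/(n-k)).

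- Size = P(|t on n-k df| > 1.96 × sqrt((n-k)/n)).
- n = 60, k = 4: 1.96 × sqrt(56/60) = 1.894, and P(|t56| > 1.894) = 6.35%.
- The normal reference alone accounts for P(|t56| > 1.96) = 5.50%. The divisor accounts for the rest.
- n = 48, k = 4: P(|t44| > 1.877) = 6.72%.
- n = 60, k = 5 or 6, if the two-way model adds a factor or interaction: 6.6% or 6.8%.
- n = 60, k = 4, at 0.0125: 1.91%. At 0.00625: 1.07%.

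**Step 2: sandwich Wald z, simulated under the null.** For a regression slope the MLR standard error is the uncorrected sandwich. With normal, uniform or skewed errors it rejected 6.1-6.5% at n = 60 and 6.6-6.9% at n = 48. With FIML and 20% of Follow-Up missing at random among 60 families, it rejected 6.6-6.9%.

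**Step 3: likelihood ratio test of condition, n = 60.** Unscaled closed form: P(F(1,56) > 56 × (exp(3.841/60) - 1)) = P(F > 3.70) = 5.94%. For the robust version the result depends on the scaling formula:

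| Errors | Trace difference including the variance parameter | Two mean-parameter formulas |
|---|---|---|
| Uniform | 5.3% | not run |
| Normal | 6.3% | 5.9-6.1% |
| Skewed | 8.0% | 5.8-6.0% |

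These are for constant error variance. When the spread rose with PRE, the first formula gave 7.3% (normal) and 9.0% (skewed).

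**Step 4: what is reported.** A t-based p of 0.050 on 56 df has t = 2.003. The MLR statistic is then 2.003 × 1.035 = 2.073, and its normal p is 0.038. Correct intervals are 1.035 × 2.003/1.96 = 1.058 times as wide, so the uncorrected ones are 1 - 1/1.058 = 5.5% too narrow.

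**Step 5: Holm, Wald z, four or eight tests, global null, complete data.**

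| Outcome correlation | n = 60 | n = 48 |
|---|---|---|
| 0.3-0.6 | 5.8-8.2% | 6.7-9.1% |
| 0.7 | 5.2-5.9% | 5.9-6.3% |
| 0.8 | 4.3-4.8% | 4.7-5.7% |

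**Step 6: the remedy.** Variance × n/(n-k) with t on n-k df rejected 4.9-5.0% with complete data, and 4.7-5.1% with FIML and 20% missing Follow-Up, taking n as the number observed. With 30 per arm and the SSI SD at 1.5 times control it rejected 5.0-5.3%.

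**Step 7: change over time.** The robust likelihood ratio test rejected 5.5% (normal) or 6.2% (skewed) with 60 pooled, and 6.3% or 7.5% with 30 in one arm. With a t reference this became 4.9-5.1% (normal), and 5.7% with 60 or 6.3% with 30 (skewed). These runs omit covariates and missing data.

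All simulations are re-implementations, not MPlus output.

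**The case against.** The strongest reply is that this is a small matter resting on inference. The SAP names the robust likelihood ratio test only for the time contrasts, and it gives neither a statistic nor a reference for condition. The excess at a single 5% test by Wald z is about 1.1-1.5 points. That stands, and it limits the weight of the point. It does not reverse the direction, because both candidate tests of condition exceeded 5% in every scenario run.

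Three stronger readings are tempting, and the documents do not support them.

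- A reader might infer that Holm fails to hold 5% in this trial. Step 5 shows that this depends on the family size and the outcome correlations. The plan states neither, and at a correlation of 0.8 with 60 families there is no excess.
- A reader might take the robust likelihood ratio test as settled at about 6%. Its size varies with error shape and scaling formula, and which formula the software applies was not checked.
- A reader might treat 1.035 and 56 df as fixed constants. They assume four mean parameters, while the SAP calls the model two-way. Five or six parameters give multipliers of 1.044 or 1.054, with 55 or 54 df.

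**Conclusion.** The concern holds as a minor one. With 30 families per arm and an uncorrected reference, the MLR test of condition is mildly anti-conservative: about 6.1-6.5% by Wald z at n = 60, about 6.7% with 48 families, and about 5.3-8.0% by robust likelihood ratio test at n = 60. The p-values passed to Holm are slightly too small, which could change a conclusion only when a result is borderline.

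This rests on a two-sided 5% level, the usual large-sample reference, and four mean parameters for the closed form. An excess in familywise error is possible but not shown. Nothing here argues against the SEM ANCOVA, FIML or a robust variance.

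**What to change.** Keep the SEM ANCOVA, FIML and MLR variance. State in the SAP that condition is tested, and its interval formed, by multiplying the MLR variance by n/(n-k) and using t on n-k degrees of freedom. Here k is the number of mean parameters actually fitted, and n is the number of families with that outcome observed. With k = 4 and n = 60 the printed standard error is multiplied by 1.035 and referred to t on 56 df; recompute k if the two-way model adds a factor or interaction. Pass these p-values to Holm, list the tests in the Holm family, and report uncorrected MLR as a sensitivity analysis. Use a t reference for the change-over-time tests.

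The cost is a sentence or two of text, with the same software, model and data. Intervals widen by 5.8% at n = 60 (7.4% at n = 48). Where the corrected test has 80% power at n = 60, the uncorrected one shows 83% at alpha 0.05 or 84% at 0.0125, so 3-4 points of apparent power go. Those points come only from the inflated error rate.

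Two limits remain. Size stays at about 5.3-5.9% if the smaller arm is also the more variable (checked with 22 SSI families at 1.5 times the SD of 30 controls). For skewed change scores a t reference reduces the excess without removing it.

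### The anxiety tests named in the SAP compare adjacent visits, not SSI with waitlist; none tests the week-four effect, and the plan does not say how a PRE-POST mean test fits with PRE as a covariate.

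*Combined protocol and SAP*

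**What the plan says.** The relevant text is in the Statistical Analysis Plan under Aim 1, which covers anxiety and anxiety impact (Aim 3 in the protocol's Specific Aims).

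- Model: "we will use two-way analyses of covariance in a structural equation modeling (SEM) framework". The two factors are not named. The estimator is a "maximum likelihood estimator with robust standard errors (MLR) as implemented in the MPlus 8.8" program.
- Covariates: "In each model, participant age, treatment condition, and the PRE-score on the outcome variable will be included as covariates".
- Tests: "Robust likelihood ratio tests will be used to examine differences between PRE and POST mean scores and POST and FOLLOW-UP mean scores". No other anxiety test is named. The SAP does not say whether these comparisons are pooled over arms, made within each arm, or made between arms.

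The hypothesis, under Specific Aims (Aim 3), is a between-arm one: "anxiety symptom severity and impairment will be significantly lower among youth who receive the refined SSI relative to youth on waitlist control". It gives no time point. On timing, the Test Phase procedures say: "Parents and youth will complete a POST evaluation one week after PRE and a Follow-Up evaluation four weeks after PRE". The primary goal in the protocol's background is to "provide short-term reductions in anxiety symptom severity and impairment while families wait for more intensive treatment".

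The opening paragraph of the SAP adds full information maximum likelihood for missing values and a Holm correction. It does not list the tests in the Holm family.

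**The concern.** There are three gaps between the hypothesis, the model and the tests.

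1. PRE has two roles. It is a conditioning variable in every model and also one side of a tested difference. A model that conditions on PRE takes the PRE values as given and has no PRE mean among its parameters. The plan does not say how the PRE-POST comparison is to be obtained.
2. The tests are not stated as arm comparisons. Treatment condition appears only in the covariate list. Entry requires a SCARED score of at least 25 on the parent or youth report, so scores may fall from PRE in both arms through regression to the mean alone. A PRE-POST test that is not an arm contrast can then be significant with no SSI effect.
3. Follow-Up is compared only with POST. An effect reached by week one and kept to week four is a success for families who are waiting, yet it leaves nothing to find in the POST-to-Follow-Up step.

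At stake is whether the prespecified tests answer the trial's question, or whether the analyst must choose the decisive contrast later.

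**Working it through.** The documents give 60 families, 30 per arm, but no alpha, power, effect size, SD or correlation. There is therefore no stated figure to reproduce. The following are assumptions: two-sided 5% per test before Holm, SD 1 at each visit, no dropout, and the correlations shown.

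**Step 1. What the model contains.** Write the planned POST model as

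POST = a + b·arm + c·age + d·PRE + e.

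The parameters are a, b, c, d and the residual variance. The PRE mean, m, is not among them. If PRE is also given a distribution with estimated mean m, then with arm and age centred the marginal POST mean is a + d·m. Equality of the PRE and POST means becomes the single constraint a + d·m = m, which can be tested on 1 df. An ordinary (not robust) likelihood-ratio test of this constraint was simulated with N = 60 and 2,000 runs per setting. With no true change it rejected 5.8% to 6.5% of the time. The test is therefore obtainable in SEM, but only after a modelling step that the plan does not state.

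**Step 2. What the arm coefficient means.** Subtract PRE from both sides:

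POST − PRE = a + b·arm + c·age + (d − 1)·PRE + e.

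The coefficient b and its standard error are unchanged. The arm coefficient of the planned ANCOVA is already the arm contrast in PRE-to-POST change. The same holds at Follow-Up. The right quantity is within reach but is not named as a test.

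**Step 3. Both arms fall, no SSI effect.** For a pooled PRE-POST test with N = 60 and a fall of 0.3 SD, SE = √(2(1 − r)/60) and power ≈ Φ(0.3/SE − 1.96).

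| r (PRE, POST) | SE | 0.3/SE | Rejects (formula) | Rejects (simulated) | Arm coefficient rejects (simulated) |
|---|---|---|---|---|---|
| 0.5 | 0.129 | 2.32 | 64% | 64% | 5.0% |
| 0.7 | 0.100 | 3.00 | 85% | 85% | 5.0% |
| 0.8 | 0.082 | 3.67 | 96% | 96% | 4.9% |

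The pooled test responds to the common fall. The arm coefficient stays at its nominal level.

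**Step 4. Effect of 0.5 SD at POST, held to Follow-Up.** Taken as an arm contrast, the POST-to-Follow-Up step has a true value of 0.5 − 0.5 = 0, so it rejects at the nominal 5%. For the PRE-adjusted arm contrast at Follow-Up, SE = √(1 − r²)·√(2/30) and power ≈ Φ(0.5/SE − 1.96). The three correlation sets (PRE-POST / PRE-Follow-Up / POST-Follow-Up) run from 0.6/0.5/0.6 through 0.7/0.6/0.75 to 0.75/0.7/0.8. Only the middle value of each enters here.

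| r (PRE, Follow-Up) | SE | 0.5/SE | Power |
|---|---|---|---|
| 0.5 | 0.224 | 2.24 | 61% |
| 0.6 | 0.207 | 2.42 | 68% |
| 0.7 | 0.184 | 2.71 | 77% |

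**Step 5. Is the week-four change lost?** No. PRE-to-Follow-Up change is the sum of the two named differences, so it can be estimated. No test of it is named.

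**The case against.** The strongest reply is that the plan names an SEM framework, in which PRE can have an estimated mean, and that treatment condition is in every model expressly to examine the influence of the SSI. On a natural reading there is a PRE-adjusted model for each of POST and Follow-Up, and its treatment coefficient is the between-arm test. The plan also cites a methods source for its model, which cannot be consulted here.

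Much of this stands. A reader might infer from the double role of PRE that the PRE-POST test is impossible. Step 1 shows that it is not. A reader might also infer that the test would be biased, for example by comparing an uncentred intercept with the PRE mean, or by treating PRE as fixed in a pooled test. The documents describe neither set-up, so no size should be attached to them. PRE as a covariate also does not block the POST-to-Follow-Up comparison.

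Nor do the documents make week four the primary time point, and the Follow-Up contrast is not always the stronger one. With 0.5 SD at both visits and PRE-POST correlations of 0.6 to 0.75, the Step 4 formula gives SE 0.207 to 0.171 and power 68% to 83% at POST, above the 61-77% at Follow-Up.

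The reply does not close the gap. The natural reading has to be supplied by the reader, because the only sentence that names tests names visit-to-visit mean differences.

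**Conclusion.** The concern holds as a mismatch between hypothesis, model and named tests. It does not hold as a claim that the tests are impossible or that the ANCOVA is invalid. PRE is both covariate and compared mean without explanation, neither named test is stated as SSI versus waitlist, and none addresses the effect from PRE to week four.

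This is more than missing detail, because following the named tests literally can mislead in both directions: significance from a common fall (64-96%), and a null second step when the benefit is kept (5% rejection, against 61-77% power for the direct contrast). The first range assumes a pooled test, which is one of the readings the plan leaves open. All these figures rest on assumed effects and correlations, with no dropout and no Holm correction. They show direction and rough size and do not predict this trial's results. The data remain fully analysable, so the change should be made but the design is not in doubt.

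**What to change.** In the SAP's anxiety analysis, replace the two adjacent mean tests with the PRE- and age-adjusted SSI-versus-waitlist contrasts at POST and at Follow-Up, and enter these in the Holm family. Either of two routes supplies them:

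- the treatment coefficient of the planned ANCOVA, fitted at each visit with PRE and age as covariates; or
- one SEM per measure with PRE, POST and Follow-Up as correlated outcomes and the arm means constrained equal at PRE. PRE then leaves the covariate list. The precision of the arm contrast is essentially the same, at the price of a few more covariance parameters.

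The SAP should name one route. Report within-arm changes and the POST-to-Follow-Up difference as estimates with confidence intervals only.

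The cost is SAP wording and Mplus syntax, with no new data. Two tests per score replace two tests per score, so the Holm family need not grow. What is given up is the formal testing of mean change over time, which becomes descriptive.
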